#### Table 1. Schedule of Events

		Days						Months Post Surgery
	Screening Within 28 Days Prior to	Treatment Visits			Post Treatment Pre-Op	Surgery	Standard of Care (SOC) Follow-up	
	Visit 1	Visit 1	Visit 2	Visit 3	Visit 4	Visit 5	Visit 6	Visits 7, 8, 9
	0	1	≥48 and previous v	$\leq$ 144 l	hours, post	≥72 hours post last treatment	≤42 days post Visit 1	1, 3, & 6 months (all can be +/-3 weeks) SOC visits
Confirmed SCC	Х							
Informed consent	X							
Inclusion/exclusion criteria	Х	X a						
Schedule study visits	Х	Х	Х	Х	Х	X		
Demographic, medical/history	X							
Physical examination, b,s	X	Xª	Xª	Xa	Xª	Х		Х
Anti-emetics		Xa	Xa	Xa	Xa			
	Х							
Oral cavity examination d	Х	X a	Xa	Xa	X a	Х		Х
Neck lymph nodes exam	Х	X a	Xa	Xa	X a	Х		Х
ECG s	Х					Х		
	Х					Х		
Clinical labs f	Х	X a		Xa		Х	Xº	
HPV s	X g							
Pregnancy test	X h	Xa			Х			
PK sampling		X i	Xj	Xj	Xi			
Tumor resection							X k	
PRV111 patch treatment		X p	X p	X p	X p			
Tumor measurements q		X a	Xa	Xa	Xa	Х		

	Screening Within 28 Days Prior to	Days				Months Post Surgery		
		Treatment Vis	its			Post Treatment Pre-Op	Surgery	Standard of Care (SOC) Follow-up
	Visit 1	Visit 1	Visit 2	Visit 3	Visit 4	Visit 5	Visit 6	Visits 7, 8, 9
	0	1	≥48 and previous v	≤ 144 h¢ isit	ours, post	≥72 hours post last treatment	≤42 days post Visit 1	1, 3, & 6 months (all can be +/-3 weeks) SOC visits
Tumor Volume change from baseline (CFB) criteria			Xa	X a	Xª	Х		
Tumor photographs		$\mathbf{X}^{1}$	X 	X 	X 	Х		
Loco-regional recurrence								Х
Technical success n		Х	Х	Х	Х			
Concomitant therapy	Х	Х	Х	Х	Х	Х		Х
AE assessment	Х	Х	Х	Х	Х	X r		

Abbreviations: AE=adverse event; ECG=electrocardiogram; HPV=human papilloma virus; ECG=electrocardiogram; YE=permeation enhancer; PK=pharmacokinetics; SCC=squamous cell carcinoma; VS=vital signs.

a Performed prior to dosing.

b If a physical exam was performed within 14 days prior to the screening visit, it does not need to be repeated at the screening.

c VS: seated blood pressure and pulse will be measured after the subject has been sitting for at least 3 minutes, respiration, temperature, height and weight will be recorded at every visit. VS will be obtained pre-dose at all visits and subject will also be monitored at 30+5 minutes, 60+5 minutes and 120+5 minutes following application of the last patch applied at Visits 1 and 4 and at 30+5 minutes post last patch application at Visits 2 and 3.

d Take photos of the tumor region for further assessment of tumor shrinkage.

f CBC and chemistry panel (creatinine to determine the creatinine clearance, BUN, LFT, electrolytes (potassium, magnesium, calcium, and sodium), urinalysis.

g Tissue will be collected at Screening but the HPV status will be ascertained at any time during the study using immunohistochemistry for p16 according to institutional clinical protocols.

h Serum pregnancy test to establish eligibility for female subjects of childbearing potential. A negative urine pregnancy test must be documented within 7 days prior to the first treatment visit, and at Visit 5.

i Visit 1 & 4: PK blood samples for total platinum collected pre- treatment (time -15 to 0 minutes), and 30±5 minutes, 60±5 minutes and 120±5 minutes post removal of last patch.

j Visit 2 & 3: PK blood samples for total platinum collected pre- treatment (time -15 to 0 minutes), and 30±5 minutes, post removal of last patch and PE application.

k Sampling for tumor and lymph nodes (if available) platinum levels.

1 Photos need to be taken prior to patch application.

m Confirmation of tumor histology by a clinical pathologist is required prior to enrollment.

n Taste of the PE solution and patch, adhesion, peel-off, residual cisplatin level in the patch.

o Performed after surgery if possible

# 4 INTRODUCTION

#### 4.1 Background of Disease

Squamous cell carcinomas (SCC) of the head and neck include tumors that occur in the oral cavity (lips, buccal mucosa, anterior tongue, floor of the mouth, hard palate, upper gingiva, lower gingiva, buccal mucosa and retromolar trigone) (Brockstein, 2016). Most lip and oral cavity cancers originate in squamous cells, the thin flat cells that line the lips and oral cavity. Risk factors for oral cancer include chronic heavy use of alcohol and tobacco, long periods of exposure to natural or artificial sunlight, and exposure to human papillomavirus (HPV). Statistics also show that males and those of low socioeconomic background are at a higher risk of developing oral cancer than other demographics (Brockstein, 2016; da Silva, 2012).

In 2017, an estimated 50,000 new cases of oral and pharynx cancer will be reported in the United States (US); approximately 11.1 adults per 100,000 will develop oral and pharynx cancer per year (National Cancer Institute, 2016). The median age of diagnosis is 62 years. The incidence of oral cancer increases with age (National Cancer Institute, 2016; National Institute of Dental and Craniofacial Research, 2016).

The 5-year survival rate for oral cancer is approximately 60%; diagnosis at an early stage significantly increases the 5-year survival rate (83% for Stage I versus 10%–22% for Stage IV) (da Silva, 2012; National Cancer Institute, 2016; National Institute of Dental and Craniofacial Research, 2014). Approximately 30% of subjects have early (Stage I or II) localized disease, with most subjects diagnosed with advanced disease (Brockstein, 2016; da Silva, 2012; National Cancer Institute, 2016).

Oral cancer has a high rate of recurrence (18%–76% for subjects who undergo standard treatment), and is considered the major cause of poor survival rates. Recurrence can vary by tumor location, with a median time to recurrence of 9.5 months (range 2–79 months) for tongue, 8 months (range 2–120 months) for buccal tumor, and 5–8 months for lip tumors (da Silva, 2012; Gurudutt, 2011; Kelner, 2014). The median time to recurrence across all oral cancer sites is 7.5 months, with most recurrences (86%) occurring within 24 months (da Silva, 2012).

Approximately 1/3 of subjects treated with surgery and adjuvant therapy will experience local or regional recurrence and/or distant metastasis. Local and regional recurrences account for up to 90% of treatment failures post-surgery and radiotherapy (da Silva, 2012). An estimated 9,700 deaths will occur due to oral and pharynx cancer in the US in 2017 (National Cancer Institute, 2016).

The treatment and management of oral cancer is dependent upon the stage of disease. Standard treatment for localized early disease is surgery with or without radiation (Brockstein, 2016). For subjects with pathologically loco-regionally advanced disease (Stage III/IV), or for those treated with surgery for early stage disease identified to have close or positive margins, or positive lymph nodes, adjuvant postoperative radiotherapy with or without chemotherapy is recommended (Brockstein, 2016). Typical treatment approaches for loco-regionally advanced disease will include neoadjuvant chemotherapy or radiotherapy, primary surgery followed by adjuvant radiotherapy or chemoradiotherapy, or chemotherapy or chemoradiotherapy without

surgery (Brockstein, 2016; da Silva, 2012; Gregoire, 2010; Marta, 2015; Seiwert, 2007). Salvage surgery, adjuvant radiation, re-irradiation, and/or palliative chemotherapy is recommended for subjects with locally recurrent disease (Milano, 2015). For subjects with locally recurrent metastatic disease, palliative chemotherapy, immunotherapy, and/or supportive care are recommended (Brockstein, 2016). The most common chemotherapy drugs for advanced oral cancer includes cisplatin, methotrexate, carboplatin, 5-fluorouracil, paclitaxel, and docetaxel, which when administered alone or in combination have been shown to provide clinical benefit with demonstrated improvement in overall survival (da Silva, 2012; Gregoire, 2010; Vermorken, 2010).

# 4.2 Privo's PRV111 Patch

PRV111 (Cisplatin Transmucosal System) is a thin, 2-layer, matrix-type, non-sterile transmucosal patch consisting of a matrix layer embedded with cisplatin loaded matrix layer (CLPs) and a non-woven fabric adhesive unidirectional backing, which is applied to the matrix layer during manufacturing (Figure 1). The patch is self-adhesive.

Figure 1. PRV111 (Cisplatin Transmucosal System)

In addition to the PRV111 drug product, a separately packaged Permeation Enhancer (PE) Powder for Reconstitution (a vial **Security Product**) to be reconstituted at the clinical site with 1 mL of Water for Injection) is used in conjunction with the PRV111 drug product. The reconstituted PE Solution is intended to improve the absorption of the cisplatin active ingredient and will be applied pre and post patch application (see Pharmacy Manual for details).

# 4.3 Rationale for Use of the Product

Privo's PRV111 is intended as a local induction chemotherapy, to improve the local control of the disease prior to surgery by shrinking the tumor size. Local cisplatin delivery may result in larger and more effective doses of cisplatin delivered to the tumor while significantly reducing or eliminating the systemic toxicities and side effects traditionally associated with intravenous (IV) cisplatin chemotherapy. If proven safe and effective for the treatment of SCC of the oral cavity, PRV111, in association with the standard care, may decrease the risk of local tumor recurrence.

Cisplatin (cis-diamminedichloroplatinum) has been approved in the US for 38 years as an antineoplastic agent and is commonly administered systemically IV as a standard of care chemotherapy for the treatment of oral cancer, alone and in combination with other chemotherapies (da Silva, 2012; Vermorken, 2007; Vermorken, 2010). However, systemic treatment with cisplatin can lead to dose-limiting toxicities (DLTs) and significant side effects, including renal toxicity, ototoxicity, and myelosuppression, which can limit the extent and duration of treatment (WG Critical Care, 2015). These side effects of IV cisplatin administration can be dose-limiting, reducing the dosage and length of cisplatin treatment for subjects. Treatment with cisplatin which is targeted to the tumor site and not administered systemically may reduce the dose-limiting systemic toxicities that are observed with IV cisplatin administration.

The antineoplastic activity of cisplatin can be primarily attributed to its ability to bind and modify nuclear and mitochondrial DNA, forming multiple intrastrand and interstrand DNA adducts, which leads to the activation of the p53 apoptotic pathway and subsequently cell death (Galluzzi, 2014; Johnstone, 2015). Cisplatin has also been linked to inducing chemokine and T-cell infiltration of tumor sites, thereby impeding tumor growth (Hong, 2011).

## 4.4 Rationale for Dose Selection

The maximum total planned PRV111 cisplatin dose if dose escalation proceeds as planned in Stage 2 (10 mg per treatment visit for 5 single patch applications, and 20 mg per treatment visit for 5 double patch applications) is approximately 9 to 18 times lower than the recommended dose of IV cisplatin (180 mg for an 80 kg person) (WG Critical Care, 2015).

Version 10 of the drug product will be used for this clinical trial since it has shown good safety and efficacy in 4 nonclinical studies. This version has the optimal dose per patch as 2 mg  $(0.5 \text{ mg/cm}^2)$  that balances the quality, drug release and uniformity of the patch.

# 5 TRIAL OBJECTIVES

#### 5.1 **Primary Objective**

• Determine a safe and efficacious dose of PRV111 (Cisplatin Transmucosal System) (cisplatin drug-loaded patch + PE) under the conditions of the trial.

#### 5.2 Secondary Objectives

- Evaluate tumor response
- Assess the safety and tolerability of the treatment
- Evaluate systemic, tumor, and lymph nodes (if available) platinum levels following administration
- Evaluate device technical success including the residual cisplatin level in the patch after the application period

# 6 INVESTIGATIONAL PLAN

# 6.1 Overall Trial Design and Plan: Description

*Study Design:* This is a 2-stage adaptive study. For Stage 1, up to 10 subjects will be enrolled for the purpose of 5 evaluable subjects for the 1st stage of the study to determine a safe and efficacious dose. For Stage 2, the target goal is 11 evaluable subjects for the efficacy analysis of the final dose. If the dose remains the same as Stage 1, Stage 2 will target 6 additional evaluable subjects but up to 21 subjects will be recruited if the dose is changed between Stage 1 and 2.

For the purpose of dose selection, tolerable dose is defined as a dose where fewer than 33% of subjects being evaluated within the safety population present with DLTs. Effective dose is determined based on the evaluable population as described in the Section 10.2.

The 2 stages of the study are described below:

*Stage 1:* Up to 10 subjects will be enrolled for the purpose of 5 evaluable subjects and undergo 3 treatment applications at each of the 4 planned treatment visits. Each treatment visit will involve application of 1 ml of the permeation enhancer and will be applied pre and post patch application (see Pharmacy Manual for details) (One ml vial of PE per visit, see Pharmacy Manual). Starting approximately 5 minutes after application of the PE, 1 or 2 patches (depending on tumor size) will be applied. A total of 3 treatment applications of patches will occur. These successive applications will span approximately 35 minutes. The 3 applications provide a total of 6 mg of cisplatin per visit (12 mg if 2 patches are applied at the same time). The 4 treatment visits will be separated by 2 to 6 days (at least 48 hours apart).

The following decisions will be made based on safety and efficacy of the dose:

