# **Dosing Rules for Stage 1:**

- 1) If fewer than 2 subjects experience DLTs, then the following scheme will be considered for Stage 2 dosing:
  - a. If fewer than or equal to 2 of the evaluable subjects have a response (as tumor volume PCFB complete response [CR], strong response [SR] or partial response [PR])) the dose will be escalated from 3 to 5 treatment applications per treatment visit for Stage 2.
  - b. If 3 or more evaluable subjects have a response (as tumor volume PCFB complete response [CR], strong response [SR] or partial response [PR])), the dose will remain the same for Stage 2 (3 applications per treatment visit).
- 2) If 2 or more subjects experience DLTs at any time during Stage 1, the following scheme will be considered for dose de-escalation in Stage 2:
  - a. If there are 5 evaluable subjects in Stage 1:
    - If out of 5 evaluable subjects, 2 or more subjects have a response (as tumor volume PCFB complete response [CR], strong response [SR] or partial response [PR])), the dose will be de-escalated to 2 applications per treatment visit.
    - If out of 5 evaluable subjects, fewer than 2 have a response (as tumor volume PCFB complete response [CR], strong response [SR] or partial response [PR])), the dose will be considered intolerable and the study will be stopped.
  - b. If Stage 1 dosing was stopped prior to having 5 evaluable subjects, the dose will be de-escalated from 3 applications to 2 applications per treatment visit.

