## 8.3 Dose Modification

If in the clinical judgment of the Medical Monitor and the PIs, clinically relevant safety issues are identified, the dose regimen (number of patches/visit and/or number of visits) may be reduced at any time during the conduct of the study.

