#### 8.4 Dose Interruption

At the Investigator's discretion, study drug may be interrupted, for reasons not related to toxicity (eg, intercurrent illness, subject scheduling conflict). Such interruption may not last more than 144 hours and may not occur more than 1 time during the subject's treatment schedule.

Subjects who experience an AE(s) requiring interruption of study drug for  $\geq$ 144 hours will be removed from treatment.

Subjects who experience a DLT will be terminated from dosing, but will remain in the study for the purpose of data collection. The DLT period will be defined as the start of treatment to 14 days after the last treatment application or the time of surgery, whichever is first.

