#### **10.2** Sample Size Determination

Safety outcomes resulting in DLT will be used during the conduct of this study to select doses being tested according to pre-defined thresholds of toxicity.

- Local and systemic safety and tolerability will be summarized using descriptive statistics.
- The number of subjects with DLTs will be capped to be fewer than 2 subjects with DLTs out of 5 new subjects enrolled.
- The treatment regimen will be deemed tolerable if fewer than a third of the subjects exposed to it present DLTs.
- Efficacy based on Tumor volume CFB criteria will be summarized, and the null hypothesis that the probability of response is at most 30%, where a response is the occurrence of CR or PR will be tested using a one-sided test exact binomial test at level 0.018.
- •
- Variables measuring technical success (including residual cisplatin level in the patch) will be summarized using descriptive statistics.

At the end of Stage 2, the following is a statistical analysis of the sample size as it pertains to efficacy:

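### In Stage 1, the two-DLT trigger and the under-one-third definition of a tolerable dose can give opposite tolerability conclusions at 7 to 10 treated subjects, and the SAP's Stage 1 rules use 6 evaluable subjects where the protocol uses 5 (minor)

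*Protocol*

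**What the plan says.** Protocol 6.1 gives a rate: "For the purpose of dose selection, tolerable dose is defined as a dose where fewer than 33% of subjects" evaluated in the safety population have DLTs. The synopsis and SAP 2.2 repeat it. Protocol 10.2, the synopsis and SAP 5.1 put it almost the same way: "The treatment regimen will be deemed tolerable if fewer than a third of the subjects exposed to it present DLTs". The safety population is everyone with at least one patch applied (Protocol 10.4.1).

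The Stage 1 dosing rules in Protocol 6.1 use a count. With fewer than 2 DLT subjects the dose is kept or escalated. Rule 2 applies when 2 or more "subjects experience DLTs at any time during Stage 1":

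- **Rule 2a, 5 evaluable subjects:** with 2 or more responses the dose drops to 2 applications per visit. With fewer than 2, "the dose will be considered intolerable and the study will be stopped".
- **Rule 2b:** "If Stage 1 dosing was stopped prior to having 5 evaluable subjects, the dose will be de-escalated".

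The number treated is not fixed, because "up to 10 subjects will be enrolled for the purpose of 5 evaluable subjects". Protocol 10.2 and SAP 5.1 also cap DLTs at fewer than 2 subjects per 5 newly enrolled.

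SAP 2.2 copies rules 2a and 2b with 6 evaluable subjects in place of 5. Elsewhere SAP 2.2 and 5.1 set Stage 1 at 5 evaluable, although the opening sentence of SAP 2.2 mentions 6 patients. SAP 7 plans no changes from the protocol.

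**The concern.** The rate is introduced as serving dose selection, so it and the count both speak to the same decision. A count of 2 has no denominator, and the number treated can run from 5 to 10. Above 6 treated, 2 DLTs fall below one third.

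Determining a safe and efficacious dose is the primary objective, and DLT incidence is part of the primary endpoint (Protocol 10.5.3). In the affected cells the same data can be reported as tolerable under 10.2 and intolerable under rule 2a. Alternatively, a dose that is tolerable by definition is abandoned without the report having an agreed way to describe it. Section 8.3 says only that the regimen "may be reduced at any time during the conduct of the study", so the visible text gives no route back up. If the choice of rule is not fixed beforehand, it will be made after the data are seen.

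The SAP's 6 is a separate slip with its own consequence. Suppose Stage 1 ends with 5 evaluable subjects, 2 or more DLTs and fewer than 2 responses. The protocol stops the study. Read literally, the SAP has not reached its 6 and de-escalates under its rule 2b.

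**Working it through.** **The plan's own figures.** With n1 = 5, r1 = 2, N = 11 and rejection at 7 or more responses, the sum over x = 3 to 5 of P(X1 = x) × P(X2 ≥ 7 − x), X2 from 6 subjects, is 0.01798 at a response rate of 0.30 and 0.96437 at 0.85. The stated 0.018 and 96.44% reproduce. The plan gives no operating characteristics for the DLT rules.

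**Where the rules disagree.** Compare X ≥ 2 (count) with X/n < 0.33 (rate):

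| Treated n | 2/n | Count | Rate |
|---|---|---|---|
| 5 | 40.0% | trigger | not tolerable |
| 6 | 33.3% | trigger | not tolerable |
| 7 | 28.6% | trigger | tolerable |
| 8 | 25.0% | trigger | tolerable |
| 9 | 22.2% | trigger | tolerable |
| 10 | 20.0% | trigger | tolerable |

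At 10 treated, 3/10 = 30.0% also conflicts. Every other count at 5 to 10 treated agrees. The choice between 33% and one third changes nothing at these sizes.

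**Can 7 or more treated with 2 DLTs occur?** It needs drop-out unrelated to DLTs, overlapping treatment without an enrolment pause, or dosing that continues after the second DLT. No visible text excludes any of these. Overlap is plausible: "The DLT period will be defined as the start of treatment to 14 days after the last treatment application" unless surgery comes first. With three gaps of 2 to 6 days, that is 6 + 14 = 20 to 18 + 14 = 32 days per subject.

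**Chance of a conflict.** Assumptions, none given in the documents: true DLT rate p from 0.10 to 0.25; drop-out d among non-DLT subjects of 0 or 0.20; one subject at a time; Stage 1 ends at 5 evaluable or 10 treated. DLT subjects are non-evaluable unless stated.

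*Stop at the second DLT, d = 0.* At most 4 subjects can be evaluable before the second DLT, so at most 6 are treated. The chance is 0.

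*Stop, d = 0.20.* The chance is the sum over n = 7 to 10 of (n − 1) p² (1 − p)^(n−2) × P(Bin(n − 2, 0.8) ≤ 4). At p = 0.25 the terms are 0.0598 + 0.0268 + 0.0099 + 0.0032 = 0.0997; at p = 0.10 the sum is 0.0445.

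*Stop, d = 0.20, DLT subjects stay evaluable.* This is possible for a DLT after the third visit, since SAP 5.2.2 requires 3 of 4 visits. Exact recursion gives 0.015 to 0.034, of which 0.012 to 0.027 have 5 evaluable.

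*Dosing continues, d = 0.* Only 2 DLTs in 7 treated can conflict: 15 p² (1 − p)^5 = 0.089 at p = 0.10 and 0.223 at p = 0.25.

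*Continues, d = 0.20.* Recursion gives 0.133 to 0.303, of which 0.114 to 0.251 have 5 evaluable.

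**Chance of the intolerable label in a conflict cell.** This also needs 5 evaluable and fewer than 2 responses, taken as independent of DLTs. P(fewer than 2 of 5) = 0.7^5 + 5 × 0.3 × 0.7^4 = 0.528 at a response rate of 0.30, and 0.0022 at 0.85.

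- Stop, DLT subjects non-evaluable: 0, because rule 2b applies.
- Stop, DLT subjects evaluable, d = 0.20, response rate 0.30: at most 0.027 × 0.528 = 0.014.
- Continues, response rate 0.30: 0.089 × 0.528 = 0.047 to 0.223 × 0.528 = 0.118 with d = 0; 0.114 × 0.528 = 0.060 to 0.251 × 0.528 = 0.133 with d = 0.20.
- Response rate 0.85, even if dosing continues: at most 0.251 × 0.0022 = 0.0006.

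**The case against.** The best reply is that the dose action is not in doubt. Section 6.1 gives a general definition and then specific decisions, and the specific rule says what happens at 2 or more DLTs. It is also the more cautious rule. The cap of fewer than 2 per 5 new subjects suggests the count was set for 5, where the two criteria agree. Section 10.2 can be read as already separating conduct (counts) from conclusion (rate). Lowering a dose observed at under a third is caution: 2/7 has an exact 95% interval of 3.7% to 71.0% and does not establish tolerability.

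Most of this stands. A reader might infer that the protocol leaves the next dose undetermined, or that the trigger is unsound. The documents do not support either inference. A reader might also take 30% as the size of the problem. That figure needs dosing to continue after a second DLT in a first-in-human study. Rule 2b, which contemplates dosing having stopped, points the other way. It does not settle the matter, because its stop is conditional, rule 2a allows for 5 evaluable with 2 or more DLTs, and Stage 1 has no plain stop sentence like the one for Stage 2b.

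Figure 2, the Stage 1 scheme, is not shown. The legend to Figure 3 says DLTs are evaluated on safety subjects, so Figure 2 may hold similar detail.

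The reply does not remove the clash of conclusions. The separation of conduct from conclusion is nowhere stated, the rate is expressly tied to dose selection, and rule 2a uses the word intolerable for cells that 10.2 calls tolerable.

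**Conclusion.** The point holds as a minor one. At 2/7, 2/8, 2/9, 2/10 and 3/10, Stage 1 data meet the definition of a tolerable dose while the count rule de-escalates or labels the dose intolerable, and no visible text ranks the two. The ambiguity concerns the reported tolerability conclusion more than the dose move.

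Under the natural reading (one at a time, stop at the second DLT) and assumed DLT rates of 10% to 25%, the chance of a conflict is 0% with no other drop-out and 4% to 10% with 20% drop-out, or 1.5% to 3.4% if DLT subjects stay evaluable. If dosing continues, it is 9% to 22% with no drop-out and 13% to 30% with 20%. With stopping, the intolerable mislabel is 0% if DLT subjects are non-evaluable and at most about 1.4% if they stay evaluable (20% drop-out, response rate 0.30). At the design response rate of 0.85 it is under 0.1% in every case. The existence of the conflict is certain from the text; its probability rests on these assumptions.

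The SAP's 6 evaluable in rules 2a and 2b is an error against the protocol, whatever the DLT rate.

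**What to change.** 1. In the synopsis, Protocol 6.1 and 10.2, and SAP 2.2 and 5.1, state that the DLT counts are cautious triggers that govern dose moves. State that the under-one-third criterion, over all subjects exposed to a dose, governs the reported tolerability conclusion, given with its exact interval. Reword the opening phrase of the definition to read *For the reported tolerability conclusion*.
2. In Stage 1 rule 2a of both documents, replace "the dose will be considered intolerable and the study will be stopped" with *the study will be stopped for DLTs with insufficient response*.
3. In SAP 2.2, Stage 1 rules 2a and 2b, change 6 evaluable to 5.

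The cost is text in two documents and one sponsor decision about which rule governs the conclusion. The triggers and the sample size do not change. The downside is that a dose with under one third DLTs may be reported as tolerable by definition but not pursued; the exact interval shows how little that label then establishes.
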